6	Agree (N=XX)	n(%)	n(%)	n(%)	n(%)	n(%)	n(%)		
	Completely Agree (N=XX)	n(%)	n(%)	n(%)	n(%)	n(%)	n(%)		
	Missing ² (N=XX)	n(%)	n(%)	n(%)	n(%)	n(%)	n(%)		
3.AIM Q3									

				Base	ine			
		Completely	Disagree	Neither	Agree	Completely		
		Disagree	N=(XX)	agree nor	(N=XX)	Agree	Missing ¹	
		N=(XX)		disagree		(N=XX)	(N=XX)	
				N=(XX)				
	Completely Disagree (N=XX)	n(%)	n(%)	n(%)	n(%)	n(%)	n(%)	
	Disagree (N=XX)	n(%)	n(%)	n(%)	n(%)	n(%)	n(%)	
Month	Neither agree nor disagree (N=XX)	n(%)	n(%)	n(%)	n(%)	n(%)	n(%)	
3	Agree (N=XX)	n(%)	n(%)	n(%)	n(%)	n(%)	n(%)	
	Completely Agree (N=XX)	n(%)	n(%)	n(%)	n(%)	n(%)	n(%)	
	Missing ² (N=XX)	n(%)	n(%)	n(%)	n(%)	n(%)	n(%)	
	Completely Disagree (N=XX)	n(%)	n(%)	n(%)	n(%)	n(%)	n(%)	
	Disagree (N=XX)	n(%)	n(%)	n(%)	n(%)	n(%)	n(%)	
Month	Neither agree nor disagree (N=XX)	n(%)	n(%)	n(%)	n(%)	n(%)	n(%)	
6	Agree (N=XX)	n(%)	n(%)	n(%)	n(%)	n(%)	n(%)	
	Completely Agree (N=XX)	n(%)	n(%)	n(%)	n(%)	n(%)	n(%)	
	Missing ² (N=XX)	n(%)	n(%)	n(%)	n(%)	n(%)	n(%)	
		Month 3						
		Completely	Disagree	Neither	Agree	Completely		
		Disagree	N=(xx)	agree nor	(N=xx)	Agree		
		N=(xx)		disagree		(N=xx)	Missing (N=XX)	
				N=(xx)				
	Completely Disagree (N=XX)	n(%)	n(%)	n(%)	n(%)	n(%)	n(%)	
	Disagree (N=XX)	n(%)	n(%)	n(%)	n(%)	n(%)	n(%)	
Month	Neither agree nor disagree (N=XX)	n(%)	n(%)	n(%)	n(%)	n(%)	n(%)	
6	Agree (N=XX)	n(%)	n(%)	n(%)	n(%)	n(%)	n(%)	
	Completely Agree (N=XX)	n(%)	n(%)	n(%)	n(%)	n(%)	n(%)	
	Missing ² (N=XX)	n(%)	n(%)	n(%)	n(%)	n(%)	n(%)	
4.AIM Q4								
		Baseline						
		Completely	Disagree	Neither	Agree	Completely		

		Disagree N=(XX)	N=(XX)	agree nor disagree N=(XX)	(N=XX)	Agree (N=XX)	Missing ¹ (N=XX)
	Completely Disagree (N=XX)	n(%)	n(%)	n(%)	n(%)	n(%)	n(%)
	Disagree (N=XX)	n(%)	n(%)	n(%)	n(%)	n(%)	n(%)
Month	Neither agree nor disagree (N=XX)	n(%)	n(%)	n(%)	n(%)	n(%)	n(%)
3	Agree (N=XX)	n(%)	n(%)	n(%)	n(%)	n(%)	n(%)
	Completely Agree (N=XX)	n(%)	n(%)	n(%)	n(%)	n(%)	n(%)
	Missing ² (N=XX)	n(%)	n(%)	n(%)	n(%)	n(%)	n(%)
	Completely Disagree (N=XX)	n(%)	n(%)	n(%)	n(%)	n(%)	n(%)
	Disagree (N=XX)	n(%)	n(%)	n(%)	n(%)	n(%)	n(%)
Month	Neither agree nor disagree (N=XX)	n(%)	n(%)	n(%)	n(%)	n(%)	n(%)
6	Agree (N=XX)	n(%)	n(%)	n(%)	n(%)	n(%)	n(%)
	Completely Agree (N=XX)	n(%)	n(%)	n(%)	n(%)	n(%)	n(%)
	Missing ² (N=XX)	n(%)	n(%)	n(%)	n(%)	n(%)	n(%)
				Mont	th 4		
		Completely	Disagree	Neither	Agree	Completely	
		Disagree	N=(xx)	agree nor	(N=xx)	Agree	Missing
		N=(xx)		disagree		(N=xx)	(N=XX)
				N=(xx)			
	Completely Disagree (N=XX)	n(%)	n(%)	n(%)	n(%)	n(%)	n(%)
	Disagree (N=XX)	n(%)	n(%)	n(%)	n(%)	n(%)	n(%)
Month	Neither agree nor disagree (N=XX)	n(%)	n(%)	n(%)	n(%)	n(%)	n(%)
8	Agree (N=XX)	n(%)	n(%)	n(%)	n(%)	n(%)	n(%)
	Completely Agree (N=XX)	n(%)	n(%)	n(%)	n(%)	n(%)	n(%)
	Missing ² (N=XX)	n(%)	n(%)	n(%)	n(%)	n(%)	n(%)

¹Missing at T1, completed at T2

Abbreviations: FIM = Feasibility of Intervention Measure

Percentage calculations: Non-missing cell %:

numerator = number selecting respective combination of Time 1 and Time 2 responses denominator = number of participants responding within Time 1 response category at Time 1

²Missing at T2, completed at T1

Table 14. Implementation Science-Related Protocol Deviations

[figure not shown]
Protocol Deviation	IS-related Protocol Deviations Reported for Expert Panel n(%)
IS-related Protocol Deviations	
Placeholder sub-category 1	
Placeholder sub-category 2	
Placeholder sub-category 3	

¹ Deviations associated with incomplete IS questionnaires are for those initiated but not completed

Note: Numerators equal the number of expert panel members experiencing respective deviation type, denominators equal the number of expert panel members in ana

8 Figures

Figure 1. Bar Chart Showing Mean HIV Care Providers/Clinical Staff FIM and AIM Responses at Baseline, Month 4 and Month 8

[figure not shown]

Abbreviations: FIM = Feasibility of Intervention Measure; AIM = Acceptability of Intervention Measure; BL=baseline; M4 = Month 4; M8 = Month 8

Error Bars = Standard error

Figure 2. Bar chart showing proportion of HIV Care Providers/Clinical Staff Responding "Agree" or Completely Agree" On All FIM Items at Baseline, Month 4, and Month 8

[figure not shown]
Abbreviations: FIM = Feasibility of Intervention Measure; BL=baseline; M4 = Month 4; M8 = Month 8 Responses: 4=CCI 5=CCI

For each time point, numerator = number responding '4' or '5', denominator = number completing all 4 items

Error Bars = Standard error

Figure 3. Bar chart showing proportion of HIV Care Providers/Clinical Staff Responding "Agree" or Completely Agree" On All AIM Items at Baseline, Month 4, and Month 8

[figure not shown]

Abbreviations: FIM = Feasibility of Intervention Measure; BL=baseline; M4 = Month 4; M8 = Month 8

Responses: 4=CCI 5=CCI

For each time point, numerator = number responding '4' or '5', denominator = number completing all 4 items Error Bars = Standard error

Figure 4. Bar chart showing change in Proportion of HIV Care Providers/Clinical Staff Responding "Agree" or Completely Agree" On All FIM Items, Baseline to Month 4, Baseline to Month 8, and Month 4 to Month 8

Abbreviations: FIM = Feasibility of Intervention Measure; BL=baseline; M4 = Month 4; M8 = Month 8

[figure not shown]
Responses: 4=CCI 5=CCI

Note: Reporting for change includes only those who completed surveys at both respective time points, which may differ from reporting at each individual timepoint. Each change row is limited to those completing all 4 items at both respective timepoints; numerator = number responding '4' or '5', denominator = number completing all 4 items

Error Bars = Standard error

Figure 5. Bar chart showing change in Proportion of HIV Care Providers/Clinical Staff Responding "Agree" or Completely Agree" On All AIM Items, Baseline to Month 4, Baseline to Month 8, and Month 4 to Month 8

Abbreviations: FIM = Feasibility of Intervention Measure; BL=baseline; M4 = Month 4; M8 = Month 8

[figure not shown]
Responses: 4=CCL , 5=CCL

Note: Reporting for change includes only those who completed surveys at both respective time points, which may differ from reporting at each individual timepoint. Each change row is limited to those completing all 4 items at both respective timepoints; numerator = number responding '4' or '5', denominator = number completing all 4 items

Error Bars = Standard error

Figure 6. Bar Chart Showing Mean Expert Panel FIM and AIM Responses at Baseline, Month 3, and Month 6

[figure not shown]

Abbreviations: FIM = Feasibility of Intervention Measure; AIM = Acceptability of Intervention Measure; BL=baseline; M3 = Month 3; M6 = Month 6

Error Bars = Standard error

Figure 7. Bar chart showing proportion of Expert Panel Responding "Agree" or Completely Agree" On All FIM Items at Baseline, Month 3, and Month 6

[figure not shown]

Abbreviations: FIM = Feasibility of Intervention Measure; BL=baseline; M3 = Month 3; M6 = Month 6

For each time point, numerator = number responding '4' or '5', denominator = number completing all 4 items

Error Bars = Standard error

Figure 8. Bar chart showing proportion of Expert Panel Responding "Agree" or Completely Agree" On All AIM Items at Baseline, Month 3, and Month 6

[figure not shown]
Abbreviations: FIM = Feasibility of Intervention Measure; BL=baseline; M3 = Month 3; M6 = Month 6

Responses: 4=CCI , 5=CCI For each time point, numerator = number responding '4' or '5', denominator = number completing all 4 items

Error Bars = Standard error

Figure 9. Bar chart showing change in Proportion of Expert Panel Responding "Agree" or Completely Agree" On All FIM Items, Baseline to Month 3, Baseline to Month 6, and Month 3 to Month 6

[figure not shown]

Note: Reporting for change includes only those who completed surveys at both respective time points, which may differ from reporting at each individual timepoint. Each change row is limited to those completing all 4 items at both respective timepoints; numerator = number responding '4' or '5', denominator = number completing all 4 items

Error Bars = Standard error

Figure 10. Bar chart showing change in Proportion of Expert Panel Responding "Agree" or Completely Agree" On All AIM Items, Baseline to Month 3, Baseline to Month 6, and Month 3 to Month 6

Abbreviations: FIM = Feasibility of Intervention Measure; BL=baseline; M3 = Month 3; M6 = Month 6

Note: Reporting for change includes only those who completed surveys at both respective time points, which may differ from reporting at each individual timepoint. Each change row is limited to those completing all 4 items at both respective timepoints; numerator = number responding '4' or '5', denominator = number completing all 4 items

Error Bars = Standard error

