Question	Number of Participants at Baseline	Response	n (%)
		Injections are not available at my provider's office	n (%)
		Other*	n (%)
		No advantages of receiving CABENUVA at the infusion center	n (%)
		Missing	n (%)
		Inconvenient location of the infusion center	n (%)
		Unfamiliar with routine at the infusion center	n (%)
		Unfamiliar with the infusion center staff	n (%)
		Inconvenient hours for the infusion center	n (%)
	XX	Less privacy at the infusion center	n (%)
		Decreased contact with my HIV provider	n (%)
3. What are the		Difficulty scheduling and rescheduling appointments	n (%)
disadvantages of going to the infusion center to receive		Too many appointments between the IC and the HIV doctors	n (%)
CABENUVA? ^{2,3}		Too many lab draws	n (%)
		Infusion center doesn't know how to manage the pain or side effects of CABENUVA	n (%)
		I don't want other people at the infusion center to know I have HIV	n (%)
		Other*	n (%)
		No disadvantages of receiving CABENUVA at the infusion center	n (%)
		Missing	n (%)
		Very Convenient	n (%)
4.How convenient is it for you to get to the infusion center for your CABENUVA visits? ¹		Somewhat convenient	n (%)
	XX	A little convenient	n (%)
		Neutral	n (%)
		A little inconvenient	n (%)

Question	Number of Participants at Baseline	Response	n (%)
		Somewhat inconvenient	n (%)
		Very inconvenient	n (%)
		Missing	n (%)
		1-15 minutes	n (%)
		16-30 minutes	n (%)
5. How long does it	N 04	31-45 minutes	n (%)
typically take you to get to the infusion center? ¹	XX	46-60 minutes	n (%)
		More than 60 minutes	n (%)
		Missing	n (%)
		Very acceptable	n (%)
	XX	Somewhat acceptable	n (%)
		A little acceptable	n (%)
6. How acceptable to you is the time it		Neutral	n (%)
typically takes you to get to the infusion center? ¹		A little unacceptable	n (%)
		Somewhat unacceptable	n (%)
		Very unacceptable	n (%)
		Missing	n (%)
		1-15 minutes	n (%)
		16-30 minutes	n (%)
7. How much time do you expect to spend in	V 0.4	31-45 minutes	n (%)
the infusion center for each CABENUVA visit?1	XX	46-60 minutes	n (%)
		More than 60 minutes	n (%)
	Ì	Missing	n (%)
8. How concerned are you about unwanted	VC.	Very concerned	n (%)
disclosure of your HIV status when attending	XX	Moderately concerned	n (%)

Question	Number of Participants at Baseline	Response	n (%)
appointments at your HIV providers office? ¹		Somewhat concerned	n (%)
·		A little concerned	n (%)
		Not at all concerned	n (%)
		Missing	n (%)
		Very concerned	n (%)

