A Phase 4, Open-label, Single-arm Study to Optimize Implementation of CABENUVA for the Treatment of HIV-1, for Administration in US Community-based Infusion Centers

*"Other" responses and open-ended text responses will be presented in an appendix

Table 1.3.1. HIV Care Provider/Clinical Staff Prospective Preferences with CABENUVA — Baseline (N=XX)

Item	Number of Participants at Baseline	Response	n (%)
	XX	All patients	n (%)
		Patients who want to start CABENUVA but prefer not to come to the HIV clinic for each injection visit	n (%)
		Patients who have had difficulty maintaining their daily oral treatment regimen	n (%)
		Patients who have concerns about disclosure of their HIV status to others	n (%)
 What types of patients do you 		Patients who feel stigmatized by their HIV	n (%)
plan to refer to an infusion		Patients with more chaotic lifestyles (variable work schedules, frequent travel, balancing work and school)	n (%)
center to		Patients with more structured lifestyles	n (%)
receive CABENUVA? ^{1,2}		Newly diagnosed (<2 years since diagnosis)	n (%)
		Treatment experienced	n (%)
		Patients already receiving CABENUVA	n (%)
		Younger patients (<35 years old)	n (%)
		Older patients (>50 years old)	n (%)
		Other*	n (%)
		Missing	n (%)
		Infusions centers have more clinic space	n (%)
		Infusion centers have more time to add visits to their schedules	n (%)
	XX	Infusion centers have more staff to manage scheduling/rescheduling appointments	n (%)
2. What are the		Infusion centers have more staff to administer it	n (%)
potential advantages of		Infusion centers have the space to store the medication	n (%)
referring		Infusion centers manage acquisition of the medication	n (%)
patients to an infusion center		Infusion center handles the logistics of administration	n (%)
for CABENUVA		Infusion centers manage the insurance verification process	n (%)
from your perspective? ^{1,2}		Infusion centers manage the insurance reimbursement	n (%)
perspective:		Convenience for the patient	n (%)
		Financial considerations for my clinic	n (%)
		Financial considerations for my clinic	n (%)
		Missing	n (%)
3. What are the	XX	Concern I won't be aware when my patient receives CABENUVA	n (%)
potential disadvantages of referring patients to an infusion center		Concern I won't be aware if my patient does not receive CABENUVA on time	n (%)
		Concern about adverse event management	n (%)
		Concern about management of injection site reactions	n (%)

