Item	Number of Participants at Baseline	Response	n (%)
for CABENUVA from your perspective? ^{1,2}		Concern about reduced involvement in management of HIV-related care	n (%)
		Inconvenience for patients; having to go to two locations (clinic for routine visits, infusion center for injections)	n (%)
		Concern patient won't want to go to infusion center	n (%)
		Concern about stigma patient may experience receiving an CABENUVA at infusion center	n (%)
		Missed opportunity for revenue for my HIV clinic	n (%)
		Issues with infusion centers handling the logistics associated with insurance verification and approval	n (%)
		Issues with infusion centers handling the logistics associated with insurance reimbursement	n (%)
		Fear of losing my patient to another provider	n (%)
		Other*	n (%)
		Missing	n (%)
	XX	Once every month	n (%)
4. If your patient is receiving CABENUVA at an infusion center,		Once after the first injection at the infusion center, then every 3 months	n (%)
		Once after the first injection at the infusion center, then every 6 months	n (%)
how often do		Once every 3 months	n (%)
you want to see them in your		Once every 6 months	n (%)
clinic for follow-		Once a year	n (%)
up? ³		Other*	n (%)
		Missing	n (%)
	XX	Once every month	n (%)
5. If your patient		Once after the first injection at the infusion center, then every 3 months	n (%)
is receiving CABENUVA at an		Once after the first injection at the infusion center, then every 6 months	n (%)
infusion center, how often do		Once every 3 months	n (%)
you want to		Once every 6 months	n (%)
them to get routine labs? ³		Once a year	n (%)
roddire labs.		Other*	n (%)
		Missing	n (%)

¹ Select all that apply

Abbreviation: HIV = human immunodeficiency virus

² Within each question, response choices will be ordered by percent endorsing, descending, and ties will go in order presented to respondents. For items with more than 5 response options, the top 5 selected response options within each item at baseline will be bolded in tables for subsequent timepoints.

³ Select one response

NOTE: Missing = the number of participants who completed any portion of a survey at any time but did not complete respective item; Missing % = the number of participants who filled out any portion of a survey at any time but did NOT complete the respective item / the number of people who filled out any portion of a survey at any time.

Cell percentages do not include missing

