		Infusion centers manage the insurance verification process	n (%)
		Infusion centers manage the insurance reimbursement	n (%)
		Convenience for the patient	n (%)
		Financial considerations for my clinic	n (%)
		Other	
		Missing	n (%)
		Concern I won't be aware when my patient receives CABENUVA	n (%)
		Concern I won't be aware if my patient does not receive CABENUVA on time	n (%)
6. What are the		Concern about adverse event management	n (%)
disadvantages of referring patients to an infusion center for CABENUVA from your perspective? ^{1,2}	XX	Concern about management of injection site reactions	n (%)
		Concern about reduced involvement in management of HIV-related care	n (%)
		Inconvenience for patients; having to go to two locations (clinic for routine visits, infusion center for injections)	
		Concern patient won't want to go to infusion center	n (%)

		Concern about stigma patient may experience receiving an CABENUVA at infusion center	n (%)
		Missed opportunity for revenue for my HIV clinic	n (%)
		Issues with infusion centers handling the logistics associated with insurance verification and approval	n (%)
		Issues with infusion centers handling the logistics associated with insurance reimbursement	n (%)
		Fear of losing my patient to another provider	n (%)
		Other*	n (%)
		Missing	n (%)
	XX	Once every month	n (%)
		Once after the first injection at the infusion center, then every 3 months	n (%)
		Once after the first injection at the infusion center, then every 6 months	n (%)
7. If a patient in your care is receiving CABENUVA at an infusion center, how often		Once every 3 months	n (%)
do you see them/expect to see them in your clinic for follow-up? ³		Once every 6 months	n (%)
		Once a year	n (%)
		Other*	n (%)
		Missing	n (%)
8. If a patient in your care is		Once every month	n (%)
receiving CABENUVA at an infusion center, how often do they get/expect to get routine labs? ³		Once after the first injection at the infusion center, then every 3 months	n (%)
		Once after the first injection at the infusion center, then every 6 months	n (%)

		Once every 3 months	n (%)
		Once every 6 months	n (%)
		Once a year	n (%)
		Other*	n (%)
		Missing	n (%)

¹ Select one response

Abbreviations: HIV = Human immunodeficiency virus

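### Provider advantages and disadvantages items have no 'none' answer; at Baseline, any blank meaning 'none' leaves the percentage base and inflates every listed option

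*SAP*

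**What the plan says.** All table references are to the provider and Expert Panel SAP unless another SAP is named.

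- **Disadvantages items.** Table 1.3.1 item 3 (Baseline) asks about "potential disadvantages of referring patients to an infusion center". Tables 1.3.2 and 1.3.3, item 6 (Months 4 and 8), ask for "disadvantages of referring patients to an infusion center for CABENUVA from your perspective". In all three the last named reason is "Fear of losing my patient to another provider", followed only by 'Other' and 'Missing'.
- **Advantages items.** Table 1.3.1 item 2 ends with "Financial considerations for my clinic" printed twice and then 'Missing', so it shows neither 'none' nor 'Other'. Tables 1.3.2 and 1.3.3, item 5, print that row once and then 'Other'. None has a 'none' row.
- **Response type.** At Baseline these items carry the footnote "Select all that apply". At Months 4 and 8 they carry footnote markers 1 and 2, which in those tables mean single response and multiple response, so the response type contradicts itself there.
- **Missing and base at Baseline.** The Table 1.3.1 note reads "Missing = the number of participants who completed any portion of a survey at any time but did not complete respective item", and adds "Cell percentages do not include missing".
- **Missing and base at Months 4 and 8.** The notes to Tables 1.3.2 and 1.3.3 define Missing among those eligible at the timepoint. They do not print the line that removes Missing from cell percentages.
- **Comparator.** In the participant SAP, Table 1.3.1 offers "No disadvantages of receiving CABENUVA at the infusion center" and an equivalent answer for advantages.

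**The concern.** These items report directly on two secondary objectives, the advantages and the disadvantages of referring patients to an infusion center (protocol Section 3; provider SAP Table A). On a multiple-response item without a 'none' answer, a blank has two meanings: nothing applies, or the question was skipped. The Missing row also takes in people who did not return that form, so three different groups share one row.

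Where Missing is removed from the base, the providers lost from the disadvantages item include those with the most favourable view of referral. Every listed disadvantage is then given as a share of a less favourable remainder. The advantages item behaves in the same way: providers who see no advantage drop out and every listed advantage rises.

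The study's other questionnaires avoid this. Besides the participant items, the staff SAP (Table 1.1.1 item 3) has an answer for having no concerns, and the Expert Panel provider form (Table 8.2.1 item 9b) has one for having met no challenges in referral.

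**Working it through.** The plan gives no percentage or precision figure for these items, so there is nothing of its own to reproduce.

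**Step 1. How can 'none' be recorded?**

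| Item | 'None' row | 'Other' row | Missing removed from base |
|---|---|---|---|
| Disadvantages, Baseline (1.3.1) | no | yes | stated |
| Disadvantages, Months 4 and 8 (1.3.2, 1.3.3) | no | yes | not stated |
| Advantages, Baseline (1.3.1) | no | no | stated |
| Advantages, Months 4 and 8 (1.3.2, 1.3.3) | no | yes | not stated |

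A 'none' written under 'Other' keeps the provider in the base, but it is counted in the 'Other' row as if it were a further advantage or disadvantage, with the text only in an appendix. No recoding rule is given. A blank takes the provider out of the Baseline base.

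**Step 2. Formula.** Let N be the providers who return the form, e the number ticking a given option, and b the blanks that mean 'none' and remain after queries. For simplicity there are no other missing answers.

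- Share of all who returned the form: e/N
- Percentage under the Table 1.3.1 rule: e/(N-b)
- Inflation factor: [e/(N-b)] / (e/N) = N/(N-b), the same for every option in the item

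**Step 3. Numbers.** N = 20 is the approximate provider number in the provider SAP Section 2 and protocol Section 6.1. The documents do not give e or b. I take e = 5, so e/N = 25.0%, and vary b from 0 to 10.

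| b | Base | Printed | Factor | Overstatement (points) |
|---|---|---|---|---|
| 0 | 20 | 25.0% | 1.00 | 0 |
| 2 | 18 | 27.8% | 1.11 | 2.8 |
| 4 | 16 | 31.25% | 1.25 | 6.25 |
| 8 | 12 | 41.7% | 1.67 | 16.7 |
| 10 | 10 | 50.0% | 2.00 | 25.0 |

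**Step 4. Effect on a comparison over time.** This step assumes that the Baseline rule also applies at Month 8, which the shell does not say. Suppose 8 of 20 tick a concern at Baseline with b = 2, and 6 of 20 tick it at Month 8 with b = 8. The tables would print 8/18 = 44% and then 6/12 = 50%. On all returned forms the shares are 8/20 = 40% and 6/20 = 30%. A fall would appear as a rise.

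**The case against.** A reader might infer that a provider with no disadvantage to report has to leave the item blank, and that every disadvantage is therefore overstated at all three timepoints. The documents do not support that.

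- 'Other' with free text is offered on every disadvantages item and on the Month 4 and Month 8 advantages items, and Table A2 is set aside for provider free text. Only the Baseline advantages item has neither route, and its duplicated row looks like a typing slip where 'Other' belongs.
- The exclusion line is printed only under Table 1.3.1. Neighbouring Month 4 and Month 8 tables (1.2.2, 1.2.3, 1.4.2, 1.4.3) do print it, so the same convention is plausible for Tables 1.3.2 and 1.3.3, but it is not stated. A footnote lost in reading the PDF cannot be ruled out.
- Section 3.1 has missing data queried with the provider. This reduces the number of blanks but does not settle the matter: a queried provider still has no 'none' box in the shell, and unanswered queries may be closed with sponsor approval.

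A reader might also infer that satisfied providers disappear from the results altogether. They do not. Tables 1.4.1 to 1.4.3 grade 16 concerns, each with a lowest category of no concern, at all three timepoints. Table 1.3.3 asks about overall satisfaction and about continuing to refer, and the objective also has Month 8 interviews. The analyses are descriptive (Section 3), no decision rule rests on these cells, and a reader given n and the Missing count can compute another base. That reader could still not separate 'none' from a skipped item or an unreturned form.

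Finally, the questionnaires themselves are not in the documents. The point rests on the table shells.

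**Conclusion.** The point holds in a conditional form. As shown in the shells, 'no advantage' or 'no disadvantage' can be recorded only as a write-in under 'Other' or as a blank, and at Baseline the advantages item shows not even 'Other'. The stated Baseline rule then removes blanks from the base, which multiplies every option by N/(N-b). At N = 20 this is a factor of 1.11 for two such blanks and 1.67 for eight. There is no bias if no such blank remains after queries. The true b is unknown, so the documents show a possible bias and not a measured one. For Months 4 and 8 the established defect is narrower: there is no 'none' answer, and the percentage base is not stated. The consequence is confined to the summaries for two secondary objectives and does not touch the primary endpoint.

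**What to change.** For the advantages and disadvantages items in Tables 1.3.1 to 1.3.3:

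1. Use as denominator all providers who returned that timepoint's questionnaire, and state this under each of the three tables.
2. Replace the single Missing row by two rows: 'no option ticked' (form returned) and 'questionnaire not returned'.
3. Code write-ins under 'Other' that amount to 'none' as their own category, and do not count them as an advantage or disadvantage.
4. Correct the duplicated row in the Baseline advantages item, and the response-type footnotes in Tables 1.3.2 and 1.3.3.
5. If any data collection remains, add a 'none' answer to each item, as the participant questionnaire has. This may be too late: the SAP is Version 3.0 of March 2024, and the staff SAP of the same date already describes some collected data in the past tense.

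For collected data the cost is footnotes, one added row per item and a short coding rule. The downside is that a genuine skip on a returned form is grouped with 'no option ticked' and stays in the base, which can slightly understate the percentages. The separate row lets the reader see how many answers are open to that doubt.
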